12. PROCEDURE FOR HANDLING PRODUCT QUALITY COMPLAINTS

A Product Quality Complaint (PQC) refers to any written, electronic, or oral communication that alleges deficiencies related to the identity, quality, durability, reliability, safety, effectiveness or performance of test articles after they have been released for clinical trial use.

Potential complaints may come from a variety of sources including but not limited to subjects, clinical research associates (CRA), clinical operations managers (COM), medical monitors, and site personnel, etc. The following are not considered product quality complaints:

- Subject satisfaction inquiries reported via “Subjective Questionnaires” and “Patient Reported Outcomes (PRO).”
- Clinical test articles that are stored improperly or damaged after receipt at the investigational site.
- Lens replacements that occur due to drops/fall-outs.
- Damage deemed by clinicians or clinical staff to be caused by handling by the user, and not indicative of a quality deficiency (i.e. tears, rips, etc.), only in situations where there is no deficiency alleged by the subject.

Within 24 hours of site personnel becoming aware that a PQC has occurred, the PQC must be recorded in the EDC system, which will trigger an automatic email notification to the appropriate COM/CRA and Clinical QA representative. In cases where the EDC system in use is not configured to send automatic notifications or when an EDC system is not used, the COM/CRA is responsible for notifying Clinical QA upon discovery that a PQC has occurred.

Upon receipt of the EDC notification, the COM/CRA will contact the study site to collect additional information which will include:

- Date the complaint was received/recorded in the EDC System (Date of Sponsor Awareness).
- Who received the complaint.
- Study number.
- Clinical site information (contact name, site ID, telephone number).
- Lot number(s).
- Unique Subject Identifier(s).
- Indication of who first observed complaint (site personnel or subject).
- OD/OS indication, along with whether the lens was inserted.
- Any related AE number if applicable.
- Detailed complaint description (scheduled/unscheduled visit, wear time, symptoms, resolution of symptoms, etc.).

Clinical Study Protocol

Johnson & Johnson Vision Care, Inc.

- Eye Care Provider objective (slit lamp) findings if applicable.
- Confirmation of product availability for return (and tracking information, if available), or rationale if product is not available for return

Once a complaint is received, it will be assessed by the COM, CRA, or trained site personnel to determine if it is an Adverse Event/Serious Adverse Event (AE/SAE). If the complaint results in an AE/SAE, the COM/CRA, or trained site personnel will follow Section 13 of this protocol. If the AE/SAE was potentially the result of a product quality related deficiency, these procedures also applies and will be executed in parallel.

In some cases, a PQC form may be generated in EDC by the site in error. In this event, the PQC forms will be marked “Intentionally Left Blank” or “ILB”. Justification for ILB must be documented.

13. ADVERSE EVENTS

13.1. Definitions and Classifications

Adverse Event (AE) – An AE is “any untoward medical occurrence, unintended disease or injury, or untoward clinical signs (including abnormal laboratory findings) in subjects, users or other persons, whether or not related to the investigational medical device.”

NOTE: This definition includes events related to the investigational medical device or the comparator, and to the procedures involved. For users or other persons, this definition is restricted to events related to investigational medical devices.¹

An AE includes any condition (including a pre-existing condition) that:

1. Was not present prior to the study, but appeared or reappeared following initiation of the study.
2. Was present prior to the study but worsened during the study. This would include any condition resulting from concomitant illnesses, reactions to concomitant medications, or progression of disease states.

NOTE: Pregnancy must be documented as an adverse event and must be reported to the clinical monitor and to the Sponsor immediately upon learning of the event.

Serious Adverse Event (SAE) – An SAE is any adverse event that led to any of the following:

- Death
- Serious deterioration in the health of the subject that resulted in any of the following:
 - Life-threatening illness or injury
 - Permanent or persistent impairment of a body structure or a body function
 - Hospitalization or prolongation of patient hospitalization
 - Medical or surgical intervention to prevent life-threatening illness or injury or permanent impairment to a body structure or a body function.
- Chronic disease

Clinical Study Protocol

Johnson & Johnson Vision Care, Inc.

- Foetal distress, foetal death or a congenital physical or mental impairment of birth defect.

Diagnoses and conditions that are considered Ocular Serious Adverse Events include, but not limited to:

- Microbial Keratitis (MK)
- Iritis (including cells in the anterior chamber)
- Permanent decrease in best spectacle corrected visual acuity equivalent to 2 acuity lines or greater
- Central Corneal Opacity
- Central Corneal Neovascularization
- Uveitis
- Endophthalmitis
- Hypopyon
- Hyphemia
- Penetration of Bowman's Membrane
- Persistent Epithelial Defect
- Limbal cell Damage leading to Conjunctivalization

Significant Adverse Events – are defined as events that are symptomatic and warrant discontinuation (temporary or permanent) of the contact lens wear

Diagnoses and conditions that are considered Ocular Significant Adverse Events include, but not limited to the following:

- Contact Lens Induced Peripheral Ulcer (CLPU)
- Significant Infiltrative Events (SIE)
- Superior Epithelial Arcuate Lesions (SEALS)
- Any Temporary Loss of > 2 Lines of BSCVA
- Other grade 3 or higher corneal findings, such as abrasions or edema
- Non-contact lens related corneal events - e.g. Epidemic Keratoconjunctivitis (EKC)
- Asymptomatic Corneal Scar
- Any corneal event which necessitates temporary lens discontinuation > 2 weeks

Non-Significant Adverse Events – are defined as those events that are usually asymptomatic and usually do not warrant discontinuation of contact lens wear but may cause a reduction in wear time. However, the Investigator may choose to prescribe treatment as a precautionary measure.

Diagnoses and conditions that are considered Ocular Non-Significant Adverse Events include, but not limited to the following:

- Non-significant Infiltrative Event (NSIE)
- Contact Lens Papillary Conjunctivitis (CLPC)
- Superficial Punctate Keratitis (SPK)
- Conjunctivitis: Bacterial, Viral, Allergic

Clinical Study Protocol

Johnson & Johnson Vision Care, Inc.

- Blepharitis
- Meibomianitis
- Contact Dermatitis
- Localized Allergic Reactions
- Any corneal event not explicitly defined as serious or significant adverse event, which necessitates temporary lens discontinuation < 2 weeks

Adverse Device Effect (ADE) – An ADE is an “adverse event related to the use of an investigational medical device.”

NOTE 1: This definition includes adverse events resulting from insufficient or inadequate instructions for use, deployment, implantation, installation, or operation, or any malfunction of the investigational medical device.

NOTE 2: This definition includes any event resulting from use error or from intentional misuse of the investigational medical device.⁹

Unanticipated Adverse Device Effect (UADE) – A UADE is any serious adverse effect on health or safety or any life-threatening problem or death caused by, or associated with, the test article, if that effect, problem, or death was not previously identified in nature, severity, or degree of incidence in the investigational plan, Investigator’s Brochure or protocol, or any other unanticipated serious problem associated with the test article that relates to the rights, safety and welfare of subjects.

13.2. Assessing Adverse Events

In conjunction with the medical monitor, the Investigator will evaluate adverse events to ensure the events are categorized correctly. Elements of categorization will include:

- Seriousness/Classifications (see definition in section 13.1).
- Causality or Relatedness – i.e. the relationship between the test article, study treatment or study procedures and the adverse event (not related, unlikely related, possibly related, or related - see definition in Section 13.2.1).
- Adverse Event Severity – Adverse event severity is used to assess the degree of intensity of the adverse event (mild, moderate, or severe - see definition in Section 13.2.2).
- Outcome – not recovered or not resolved, recovering or resolving, recovered or resolved with sequelae, recovered or resolved, death related to adverse event, or unknown.
- Actions Taken – none, temporarily discontinued, permanently discontinued, or other.

13.2.1. Causality Assessment

Causality Assessment – A determination of the relationship between an adverse event and the test article. The test article relationship for each adverse event should be determined by the investigator using these explanations:

- Not Related- An adverse event that is not related to the use of the test article, study treatment or study procedures.

Clinical Study Protocol

Johnson & Johnson Vision Care, Inc.

- Unlikely Related – An adverse event for which an alternative explanation is more likely, e.g. concomitant treatment, concomitant disease(s), or the relationship of time suggests that a causal relationship is not likely.
- Possibly Related – An adverse event that might be due to the use of the test article, or to the study treatment or study procedures. An alternative explanation, e.g. concomitant treatment, concomitant disease(s), is inconclusive. The relationship in time is reasonable. Therefore, the causal relationship cannot be excluded.
- Related – An adverse event that is listed as a possible adverse effect (device) or adverse reaction (drug) and cannot be reasonably explained by an alternative explanation, e.g. concomitant treatment of concomitant disease(s). The relationship in time is very suggestive, e.g. it is confirmed by de-challenge and re-challenge.

13.2.2. Severity Assessment

Severity Assessment – A qualitative assessment of the degree of intensity of an adverse event as determined by the Investigator or reported to him/her by the subject. The assessment of severity is made irrespective of test article, study treatment or study procedure relationship or seriousness of the event and should be evaluated according to the following scale:

- Mild – Event is noticeable to the subject but is easily tolerated and does not interfere with the subject's daily activities.
- Moderate – Event is bothersome, possible requiring additional therapy, and may interfere with the subject's daily activities.
- Severe – Event is intolerable, necessitates additional therapy or alteration of therapy and interferes with the subject's daily activities.

13.3. Documentation and Follow-Up of Adverse Events

The recording and documenting of adverse events (ocular and non-ocular) begin when the subjects are exposed to the test article, study treatment or study procedure. Adverse events reported before the use of test article, start of study treatment, or study procedures will be recorded as medical history. However, if the condition deteriorates at any time during the study it will be recorded and reported as an AE. Untoward medical events reported after the subject's exit from the study will be recorded as adverse events at the discretion of the Investigator.

Upon finding an adverse event, the Principal Investigator will document the condition in the subject record and in the eCRFs and complete the Adverse Event eCRF.

Complete descriptions of all adverse events must be available in the subject record. All Adverse Events including local and systemic reactions not meeting the criteria for "serious adverse events" shall be captured on the appropriate case report form or electronic data system. All adverse events occurring while the subject is enrolled in the study must be documented appropriately regardless of relationship.

It is the Investigator's responsibility to maintain documentation of each reported adverse event. All adverse events will be followed in accordance with applicable licensing requirements. Such documentation will include the following:

- Adverse event (diagnosis not symptom).

Clinical Study Protocol **Johnson & Johnson Vision Care, Inc.**

- Drawings or photographs (where appropriate) that detail the finding (e.g., size, location, and depth, etc.).
- Date the clinical site was notified.
- Date and time of onset.
- Date and time of resolution.
- Adverse event classification, severity, and relationship to test articles, as applicable.
- Treatment regimen instituted (where appropriate), including concomitant medications prescribed, in accordance with applicable licensing requirements.
- Any referral to another health care provider if needed.
- Outcome, ocular damage (if any).
- Likely etiology.
- Best corrected visual acuity at the discovery of the event and upon conclusion of the event, if the AE is related to the visual system.

Upon discovery of an AE that is deemed ‘possibly related’ or ‘related’ to the test article or study procedures (whether related to the visual system or not), an AE review form [REDACTED] must be completed. Additional dated and initialed entries should be made at follow-up evaluations. Separate forms must be completed for each eye if the AE is bilateral.

In addition, if an infiltrate(s) is present, he/she will complete the Corneal Infiltrate Assessment eCRF. Where necessary, a culture of the corneal lesion will be collected to determine if the infection is microbial in nature. If cultures are collected, the date of culture collection and laboratory utilized will be recorded.

Changes in the severity of an AE shall be documented to allow an assessment of the duration of the event at each level of intensity to be performed. Adverse events characterized as intermittent require documentation of the onset and duration of each episode. Changes in the assessment of relationship to the Test Article shall also be clearly documented.

Subjects who present with an adverse event shall be followed by the Investigator, within licensure, until all signs and symptoms have returned to pre-treatment status, stabilized, or been satisfactorily resolved. If further treatment beyond licensure is required, the patient will be referred to the appropriate health care provider. The Investigator will use his/her clinical judgment as to whether a subject reporting with an adverse event will continue in the study. If a subject is discontinued from the study, it will be the responsibility of the Investigator to record the reason for discontinuation. The Investigator will also document the adverse event appropriately and complete the Adverse Event eCRF. Any subjects with ongoing adverse events related to the test article, study treatment or study procedures, as of the final study visit date, should be followed to resolution of the adverse event or until referral to an appropriate health care provider, as recommended by the Investigator. Non-ocular adverse events that are not related to the test article, study treatment, or study procedures may be recorded as “ongoing” without further follow-up.

Clinical Study Protocol

Johnson & Johnson Vision Care, Inc.

13.4. Reporting Adverse Events

The Investigator will notify the Sponsor of an adverse event by e-mail, facsimile, or telephone as soon as possible and no later than 24 hours from discovery for any serious /significant adverse events, and 2 days from discovery for any non-significant adverse event. In addition, a written report will be submitted by the Principal Investigator to the IEC/IRB according to their requirements (Section 13.4.2). The report will comment whether the adverse event was considered to be related to the test article, study treatment or study procedures.

13.4.1. Reporting Adverse Events to Sponsor

Serious/Significant Adverse Events

The Investigator will inform the sponsor of all serious/significant adverse events occurring during the study period as soon as possible by e-mail or telephone, but no later than 24 hours following discovery of the event. The Investigator is obligated to pursue and obtain information requested by the Sponsor in addition to that information reported on the eCRF. All subjects experiencing a serious/significant adverse event must be followed up and all outcomes must be reported.

When medically necessary, the Investigator may break the randomization code to determine the identity of the treatment that the subject received. The Sponsor and study monitor should be notified prior to unmasking the test articles.

In the event of a serious/significant adverse event, the Investigator must:

- Notify the Sponsor immediately.
- Obtain and maintain in the subject's records all pertinent medical information and medical judgment for colleagues who assisted in the treatment and follow-up of the subject.
- Provide the Sponsor with a complete case history which includes a statement as to whether the event was or was not related to the use of the test article.
- Notify the IEC/IRB as required by the IEC/IRB reporting procedure according to national regulations.

Unanticipated (Serious) Adverse Device Effect (UADE)

In the event of an Unanticipated (Serious) Adverse Device Effect (UADE), the Investigator will submit a report of the UADE to the Sponsor and IEC/IRB as soon as possible, but no later than 24 hours after the Investigator first learns of the effect. This report is in addition to the immediate notification mentioned above.

The Sponsor must conduct an evaluation of the UADE and must report the results of the evaluation to FDA, the IEC/IRB and participating Investigators within 10 working days after the Sponsor first receives notification of the effect.

Non-Serious Adverse Events

All non-serious adverse events, including non-serious adverse device effects, will be reported to the sponsor by the Investigator no later than 2 days from discovery.

Clinical Study Protocol

Johnson & Johnson Vision Care, Inc.

13.4.2. Reporting Adverse Events to the Responsible IEC/IRB and Health Authorities

Adverse events that meet the IEC/IRB requirements for reporting must be reported within the IEC/IRB's written guidelines. Each clinical site will refer to and follow any guidelines set forth by their Approving IEC/IRB. Each clinical site will refer to and follow any guidelines set forth by their local governing Health Authorities.

The Sponsor will report applicable Adverse Events to the local health authorities according to the written guidelines, including reporting timelines.

13.5. Event of Special Interest

None

13.6. Reporting of Pregnancy

Subjects reporting pregnancy (by self-report) during the study will be discontinued after the event is recorded as an Adverse Event. Once discontinued, pregnant participants and their fetuses will not be monitored for study related purposes. Pregnant participants are not discontinued from contact lens or solution related studies for safety concerns, but due to general concerns relating to pregnancy and contact lens use. Specifically, pregnant women are discontinued due to fluctuations in refractive error and/or visual acuity that occur secondary to systemic hormonal changes, and not due to unforeseen health risks to the mother or fetus.

14. STATISTICAL METHODS

14.1. General Considerations

Statistical Analysis will be undertaken by the sponsor or under the authority of the sponsor. A general description of the statistical methods to be implemented in this clinical trial is outlined below.

All data summaries and statistical analyses will be performed using the Statistical Analysis System (SAS) software Version 9.4 or higher (SAS Institute, Cary, NC).¹¹ Throughout the analysis of data, the results for each subject/eye will be used when available for summarization and statistical analysis. Unscheduled visits will be summarized.

Summary tables (descriptive statistics and/or frequency tables) will be provided for all baseline variables, efficacy variables and safety variables as appropriate. Continuous variables will be summarized with descriptive statistics (n, mean, standard deviation [SD], median, minimum and maximum). Frequency count and percentage of subjects or eyes within each category will be provided for categorical data. Summary tables will be summarized by timepoint, group and lens.

14.2. Sample Size Justification

This study was designed and powered to test that the percentage of lens fit with absolute rotation for both study lenses is superior to 80% 15-minutes after insertion. The sample size

Clinical Study Protocol

Johnson & Johnson Vision Care, Inc.

was calculated using a 2-sided type I error rate of 5% with at least 80% statistical power. Historical data from [REDACTED] and [REDACTED] was both utilized in estimation of the sample size.^{7,12} Table 6 below provides details regarding each clinical study and Table 7 summarizes the absolute rotation for each study and lens for all lens fits (including any modifications).

Table 6 Summary of Historical Clinical Studies

Study ID	Design	Population	Age Range (years)	Number Enrolled	Number Dispensed	Number Completed
[REDACTED]	Single arm	Hyperopes + Myopes	40 to 70	95	86	84
[REDACTED]	2x2 crossover	Myopes	18 to 39	103	98	93

Table 7 Summary of Absolute Rotation by Lens – 15-Minutes After Insertion

	AOFA N=202	Aurora A		
		Hyperopes N=114	Myopes N=136	Total N=250
Absolute rotation n(%)				
0 to 5	174 (86.1)	85 (74.6)	96 (70.6)	181 (72.4)
>5 to 10	19 (9.4)	14 (12.3)	21 (15.4)	35 (14.0)
>10 to 15	8 (4.0)	7 (6.1)	11 (8.1)	18 (7.2)
>15	1 (0.5)	8 (7.0)	8 (5.9)	16 (6.4)
Total	202	114	136	250
Absolute rotation < 10° n(%)				
Yes	193 (95.6)	99 (86.8)	117 (86.0)	216 (86.4)
No	9 (4.5)	15 (13.2)	19 (14.0)	34 (13.6)
Total	202	114	136	250

N=Number of lens fits.

Based on the results from [REDACTED], the lens design was modified to improve the absolute rotation. The changes implemented into the lens design are more closely aligned with the Acuvue Oasys for Astigmatism lens design utilized in [REDACTED]. However, as indicated in Table 5, [REDACTED] enrolled non-presbyopic myopic subjects only. In general, presbyopic subjects have been found to more contact lens rotation compared to non-presbyopic subjects, therefore,

Clinical Study Protocol **Johnson & Johnson Vision Care, Inc.**

results from both studies were considered when choosing different scenarios of reference rates.^{7,12}

Shown in Table 6 above, [REDACTED] had rates of 86% and 96%, respectively. Therefore, different scenarios used for the sample size and power calculations were chosen within that range. Furthermore, taking into consideration that this study will enroll subjects aged 40 to 70, more conservative rates of 88%, 89% and 90% were used.^{7,12}

Sample size estimates were carried out using Monte Carlo methods. A total of 2000 boot-strap samples were simulated using different scenarios for the reference rate for event Y and interclass correlations of 0.80 to model the covariance between the left and right eyes within the same treatment, and 0.50 to model both the covariance between treatments within the same eye as well as between eyes and treatments. Each boot-strap sample was analyzed using a generalized linear mixed model with a binary distribution and the logit and the link function. Lens was included as the only fixed effect. Errors between measurements within the same subject and period were modeled using a variance component covariance structure (VC). The Kenward and Roger Method was used for the denominator degrees of freedom.¹³ The percentage of lens fits with absolute rotation less than 10° was constructed using 95% confidence intervals for the least-square mean. Success for each boot-strap sample was declared if the lower limit of the 95% CI was above 80%. Table 8 below displays the number of subjects required to test superiority for the primary hypothesis for each study lens.

While subjects will wear the study lenses in a random order data collected during evaluations in period 2 are not expected to be influenced by the lenses worn during period 1 since a wash-out 15 -minutes will be utilized between study lenses and, subjects' absolute rotation depends on the study lens on eye at that moment of data collection.

Table 8 Statistical Power for 80 Subjects to complete by Reference Rate

	Reference Rate		
	88%	89%	90%
Statistical Power (%)	87.7	95.1	98.3

Up to 90 subjects (45 Hyperopes and 45 Myopes) will be enrolled with the target of 80 subjects (40 Hyperopes and 40 Myopes) to complete the study. Since this is a single-visit, non-dispensing study, a high rate (> 10%) of subject drop-out is not expected to occur. However, subject drop-out rate will be monitored. If an unexpectedly high dropout rate is observed, then enrollment maybe be increased to ensure the minimum number of subjects required to test the primary hypothesis complete the study.

Clinical Study Protocol

Johnson & Johnson Vision Care, Inc.

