2.3. Hypotheses

Primary Hypothesis

1. Approximately 15-minutes after lens insertion, the percentage of lens fits with absolute rotation less than or equal to 10 degrees will be superior to 80%.

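### Table 8 is not per-lens power at the stated error rate: with false claims held to 2.5%, power is about 47–58%, 58–71% and 70–81% at true rates of 88%, 89% and 90%

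*Combined protocol and SAP*

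**What the plan says.** Section 2.3 states one hypothesis: "the percentage of lens fits with absolute rotation less than or equal to 10 degrees will be superior to 80" percent. Section 14.2 says the study is powered to show that "the percentage of lens fit with absolute rotation for both study lenses is superior to 80% 15-minutes after insertion", and that the sample size "was calculated using a 2-sided type I error rate of 5% with at least 80% statistical power". Section 14.4 repeats the error rate.

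The simulation in Section 14.2 uses "interclass correlations of 0.80 to model the covariance between the left and right eyes within the same treatment", and 0.50 between treatments. Its model is a logit mixed model in which "Lens was included as the only fixed effect", with a variance-components (VC) structure for errors within subject and period. The percentage "was constructed using 95% confidence intervals for the least-square mean", and a replicate succeeds if the lower limit exceeds 80%. Table 8 is tied to single lenses ("Table 8 below displays the number of subjects required to test superiority for the primary hypothesis for each study lens") and gives 87.7%, 95.1% and 98.3% at 88%, 89% and 90%. No false-claim rate at a true 80% is given.

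Section 14.5 plans a different model: sequence, period and lens as fixed effects, random site and subject, and an unstructured between-eye covariance. It pools the two lenses only if no fixed effect is significant.

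**The concern.** Two eyes correlated at 0.80 carry much less information than two independent eyes, so 160 fits per lens in 80 subjects should not give 87.7% power to separate 88% from 80%. The claim of at least 80% power is the justification for the sample size. If Table 8 is not per-lens power at the stated error rate, that justification fails at some or all of the assumed rates. A reader cannot see this, because the table shows power without the false-claim rate of the same rule.

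The unit of success is also unsettled. The text refers in different places to each lens, to both lenses, and to one percentage that is pooled conditionally, and these have different power.

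**Working it through.** **Inputs.** 80 completers (Table 8). Four lenses per subject (Section 6.1), so 160 fits per lens type and 320 in all. Null 80%; true rates 88%, 89%, 90%; correlations 0.80 and 0.50 (Section 14.2). A 2-sided 5% level allows 2.5% false superiority claims (Section 14.4). The plan does not say whether the correlations apply to the binary outcome or to a latent normal variable, so both are shown. A latent 0.80 corresponds to a binary correlation of about 0.51–0.56.

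**Can Table 8 be reproduced?** Not by any per-lens calculation that keeps both the correlations and the 2.5% level. The closest simple formula is a Wald calculation on 160 independent eyes:

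Φ((p − 0.80)/√(p(1−p)/160) − 1.96) = Φ(1.15), Φ(1.68), Φ(2.26) = 87.6%, 95.3%, 98.8%.

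That drops the correlations, and it is offered only as a question for the sponsor. The corresponding rule (at least 137 of 160) has exact power 85.2%, 92.8%, 97.1% and a false-claim rate of 4.3% under independence, or 8.6–10.4% under the stated correlations. Simulation noise does not explain the gap: with 2000 replicates the standard error at 87.7% is √(0.877 × 0.123/2000) = 0.7 points.

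**Upper bound, ignoring correlation.** With 160 independent fits, the smallest count that at most 2.5% of trials reach at a true 80% is 139 (attained 1.6%). Exact power is 71.9%, 83.8%, 92.2%. A normal approximation using the full 2.5% gives 75.8%, 87.1%, 94.6%. Both are below Table 8 in every column, and positive correlation lowers them further.

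**Closed form with correlation.** Power = Φ((p − 0.80 − 1.96√(0.16/n₀))/√(p(1−p)/n₁)), where n₀ and n₁ are the effective sample sizes under the null and the alternative.

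- Binary scale: n₀ = n₁ = 160/1.80 = 89. At 88%, (0.08 − 0.0832)/0.0345 = −0.09, so power is 46%. At 89% and 90% it is 58% and 70%.
- Latent scale: effective n is 103–106, giving 53%, 66%, 78%.

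**Simulation with false claims held to 2.5%.** 80 subjects with four correlated fits each; critical value set so that at most 2.5% pass at a true marginal 80%. R-side means the VC structure acts on residuals (independent fits); G-side means it acts on random effects.

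| Per-lens reading | Power at 88 / 89 / 90% |
|---|---|
| Clustered interval, binary | 49 / 61 / 72 |
| Clustered interval, latent | 57 / 69 / 80 |
| R-side VC, binary | 47 / 58 / 70 |
| R-side VC, latent | 54 / 66 / 78 |
| G-side subject-by-period, latent | 58 / 71 / 80–81 |
| G-side subject, latent | 55 / 67 / 76–77 |

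If both lenses must pass, power is 31–39 / 43–55 / 57–68%. Pooled (clustered or R-side), simulation gives about 61–75 / 73–85 / 82–93%. The closed form, with effective n = 320/2.8 = 114 (binary) or 149–159 (latent), gives 59 / 72 / 83% or 73 / 85 / 93%.

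**The same readings at the nominal 95% interval.** Ranges run from logit to probability intervals unless noted.

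| Reading | Power at 88 / 89 / 90% | False claims at a true 80% |
|---|---|---|
| Table 8 | 87.7 / 95.1 / 98.3 | not reported |
| Clustered, per lens, binary | 44–62 / 56–72 / 67–82 | about 2–4% |
| Clustered, per lens, latent | 54–68 / 66–78 / 77–87 | about 2–4% |
| R-side VC, per lens | 68–80 / 77–88 / 86–94 | 4–10% |
| G-side subject-by-period, per lens, latent | 78.7–87.7 / 87.4–93.1 / 92.8–96.8 | 7.6–13.5% |
| G-side subject, per lens, latent | 85.7–92.5 / 91.8–95.8 / 95.5–98.0 | 13.9–22.4% |
| R-side VC, pooled, logit only | 87–90 / 93–96 / 97–98 | 8–11% |

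The G-side readings pass too often because their least-square mean is a subject-conditional probability. It averages 82–84% when the true percentage of fits is 80%.

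**The case against.** The plan defines success by the nominal 95% interval, and Table 8 reports the power of that rule. Nothing in the plan calls for recalibrating it at a true marginal 80%. Under the nominal rule, a G-side subject-by-period fit with a probability interval gives 87.7 / 93.1 / 96.8%, close to Table 8, and Section 14.5 does use a G-side subject effect. A pooled R-side fit covers or nearly covers all three cells, and Sections 2.3 and 14.5 both speak of a single percentage. The G-side figures here come from approximate pseudo-likelihood fits with t on 79 degrees of freedom, not SAS with Kenward–Roger. Under binary-scale correlations those fits converged too rarely to use.

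Much of this stands. Table 8 may be a correct output of a rule that the text does not fully specify, and the G-side false-claim rates are approximate. But Sections 14.2 and 14.4 promise a 5% 2-sided error rate, the hypothesis concerns the percentage of lens fits, and the assumed rates were chosen from raw lens-fit percentages in Table 7. Power at that error rate is therefore the relevant figure. The literal R-side per-lens reading at the nominal interval is still below Table 8 in every cell. The readings that come near Table 8 have false-claim rates of about 8% or more. The independent-fits bound needs no mixed model.

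**Conclusion.** The concern holds. At the stated error rate and correlations, per-lens power with 80 completers is about 47–58% at 88%, 58–71% at 89% and 70–81% at 90%, against 87.7%, 95.1% and 98.3% in Table 8. Per lens, the 80% target is missed at 88% and 89% and is borderline at 90%. If both lenses must pass, it is missed at all three rates. If the lenses are pooled, it is missed at 88%, depends on the correlation scale at 89%, and is met at 90%.

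The ranges cover both scales of the correlations and the covariance readings tried. They assume that the error rate refers to the marginal percentage of fits. The G-side entries are latent-scale only, with 92–100% of fits converging; counting every non-converged replicate as a pass gives at most 58.5 / 72.1 / 81.7%. The closed-form, clustered and R-side results do not depend on those fits. Why Table 8 differs is not established.

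**What to change.** In Section 14.2:

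1. State whether success means each lens, both lenses or a pooled estimate, and make Sections 2.3 and 14.5 agree.
2. State whether 0.80 and 0.50 are binary or latent correlations, whether VC is R-side or G-side, and whether the interval is formed on the logit or probability scale.
3. Re-run the simulation with the Section 14.5 model and decision rule, including its conditional pooling if that is kept.
4. Report the type I error at a true marginal rate of 80% beside the power.
5. Replace Table 8 and the statement of at least 80% power with the results.

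The cost is one re-run simulation and probably a less favourable stated power. No extra subjects are required. For scale only, 80% per-lens power at 88% with false claims held to 2.5% would need about 130–135 completers (latent correlations) or 155 (binary).
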